12.6.2 Expected Adverse Events: Interferon gamma

Expected toxicities attributable to interferon gamma and considered exceptions to criteria for discontinuation include transient inflammatory responses (Fever, rash, flu like symptoms, **outlined in 7.1**) resulting in Grade 3 or 4 toxicities that return to baseline within 2 weeks.

12.6.3 Expected Adverse Events: Avelumab or pembrolizumab

Expected toxicities attributable to anti-PD-L1 (avelumab) or anti-PD-1 (pembrolizumab) infusions and considered exceptions to criteria for discontinuation include infusion-related reactions with Transient (\leq 24 hours) Grade 3-4 toxicity (outlined in 7.3) that resolved to \leq Grade 1. Patients with infusion reactions to avelumab will be able to receive pembrolizumab for future infusions. Patients with infusion reactions to pembrolizumab will not be able to receive avelumab for future infusions.

12.7 Adverse Event Reporting Requirements

12.7.1 Reporting to IRB

The investigator or designee must report events to the Fred Hutch IRB in accordance with the policies of the IRB.

12.7.2 Reporting to Sponsor

Classification of an event as serious or non-serious determines the reporting procedures to be followed by the site for reporting the event to the IND Sponsor.

PI to IND Sponsor Reporting Requirements for Adverse Events

Classification		Reporting Time	Reporting Action	Contact Information
Serious Adverse Event (SAE)	Fatal or life-threatening	Within 24 hours of research team* awareness	Email notification to Sponsor's Medical Monitor & ISIOC Administrator	Medical Monitor email: [contact] ISIOC email: [contact]
	All SAEs	Within 2 business days of research team* awareness	Submit completed Institution-Sponsored IND SAE Reporting Form signed by PI or designated sub-Investigator	ISIOC email: [contact]
Non-serious AE		Per CRF completion guidelines	Record information on appropriate CRFs	N/A

*Research team is defined as the individuals listed on the delegation of authority log. Physicians listed on the study's delegation of authority log as attending physicians with delegated authority to administer informed consent will not be considered part of the research team unless additional responsibilities related to the conduct of the study have been delegated to them by the Principal Investigator.

The sponsor assumes responsibility for IND safety reporting to the FDA and participating investigators, in accordance with regulations under 21 CFR 312.32.

The information in the Institution-Sponsored IND SAE Reporting Form must match or be reconciled with the information recorded in the adverse events section on the CRF and study database. For example, the same adverse event term should be used on both forms.

Each serious adverse event report received from the investigator will be evaluated by the Medical Monitor who will assess the seriousness of the event, the expectedness of the event, and the relationship to participation in the study, after reviewing the assessments and supporting documentation provided by the PI. For regulatory reporting purposes, the IND Sponsor will independently determine expectedness relating to the investigational product using safety information specified in the Investigator Brochure, the consent document and the protocol document. An event will be classified as related if either the investigator or the IND Sponsor determines that the event may be related to the study drug.

The IND Sponsor or designee will provide all investigators with a safety letter notifying them of an event that meets FDA IND Safety Reporting criteria. Investigators will be requested to provide written notification of safety report to the Fred Hutch IRB as soon as is practical, consistent with IRB requirements.

13. STATISTICAL CONSIDERATIONS

13.1 Sample size and Power

Our study is a phase I/II, non-blinded interventional trial. Our target sample size is up to 16 patients (8 per year/2 years). This target is chosen for three reasons: it is achievable from an enrollment standpoint (our clinic sees between 15-20 potentially eligible patients per year), it is logistically possible from a funding and cell processing facility standpoint, and it allows >80% power to observe a statistically significant (at one-sided 0.05 level) efficacy signal that is clinically meaningful. (see below for details). With the eligibility expansion, we expect roughly 12 patients will receive a PD1 checkpoint inhibitor. For some analyses, all 16 patients will be analyzed, yet some analyses will be restricted to patients who receive a PD1 checkpoint inhibitor. See below for the impact of this on statistical power.

13.2 Primary Endpoint: Safety

13.2.1 Definition of treatment related adverse event

For the purposes of statistical analysis and estimation of toxicity rate, a safety event will be any grade 3 or higher adverse event determined to be possibly, probably, or definitely secondary to any of the study treatments, except as expected in **Sections 12.5 and 12.6**. Please see **Section 12.1** for adverse event definition.

13.2.2 Definition of success and probability of suspension

Platinum-based combination chemotherapy is associated with 30 to 40% grade ≥ 3 toxicities⁴⁶ and although data are not yet available for MCC, combination checkpoint inhibitors see 45-55% treatment associated grade ≥ 3 toxicity in patients with metastatic melanoma.⁶⁹ To avoid exceeding these toxicity

rates, the treatment will be considered to have an acceptable safety profile if the observed toxicity rate is consistent with a true rate that does not exceed 40%.

Evidence of excessive toxicity will be an observed proportion of toxicities for which the associated lower 80% confidence limit exceeds 40%. Operationally, this limit will be met if any of the following proportions is observed: 2/2, 3/3-4, 4/5-6, 5/7-8, 6/9-10, 7/11-12, 8/13-14, 9/15-16. Under these rules, if the true probability of toxicity is 20%, the probability of suspension is approximately 0.06. If the true probability of toxicity is 60%, the probability of suspension is approximately 0.84 (based on 5,000 simulations).

The initial three part I patients will be treated and followed for toxicity. All three of these patients will receive their first cycle of treatment (T cell infusions) before additional patients will be enrolled. If zero or one of the first three part I patients experiences treatment-related and grade ≥ 3 toxicity, the remaining (up to) 13 pts will be treated on the part II portion of the trial. If instead two or more of the first three patients experience grade 3 toxicity, at the point that the two toxicities occur, the trial will be suspended and, after a detailed review of the potential causes of toxicity, consideration given to changing the cell dose or construct pending DSMB review. If any of the first three patients experience treatment related death, the trial will be suspended and, after a detailed review of the potential causes of toxicity, consideration given to changing the cell dose or construct pending DSMB review. As detailed in **Section 11.7**, if at any point any patient experiences grade 3 or higher treatment-related toxicity, that particular patient will no longer receive study related active therapies, except as specified in **Section 12.6.1**. They will continue to be followed for response and outcome.

The above toxicity considerations above will be examined among all patients, regardless of their PD1-contraindication status and whether they get PD-1/PD-L1 inhibition therapy on the trial. The delay of PD-1/PD-L1 inhibition until 14 days after T cell infusion will help differentiate toxicity related specifically to PD-1 axis inhibition. However, if any patient who does not receive a checkpoint inhibitor develops a toxicity, enrollment to such patients will be suspended pending review by the DSMB and the PI, at which point a decision will be made to continue the trial as is, modify the trial, and halt enrollment of patients for whom a checkpoint inhibitor is contraindicated.

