avelumab or pembrolizumab (PD-L1 and PD-1 inhibitors approved by the FDA for treatment of Merkel Cell Carcinoma), and class I MHC upregulation in the tumor tissue with interferon gamma. In part I (until safety demonstrated in 3 consecutive participants), participants will receive a lower dose of T cells for first infusion (5-fold dose reduction from target dose). If adequate safety profile is observed, we will proceed to part II; if adverse safety signal is seen, we will re-design trial in consultation with our DSMB and restart part I. In part II, participants will receive full dose of T cells for both infusions. We anticipate enrolling up to 16 HLA-A02+ participants with Merkel cell polyomavirus positive advanced MCC over 2 years.

We hope that study participation will provide direct benefits to the treated patients. This study will also benefit the research field for immunotherapy development for MCC and cancer more generally. Merkel cell carcinoma is an ideal cancer in which to develop immunotherapies due to the target of the viral oncoprotein which is immunodominant. This allows us to give T cells that are more on-target (with less risk of immune related adverse events; iRAEs) and also to more closely monitor immune responses to the cancer. If treatment is successful, as we are hopeful based on our early success with similar approaches as above, similar regimens could be expanded to other malignancies. If treatment is unsuccessful, our sophisticated immunological monitoring of the infused cells, native immune cells, and tumor tissues will allow for a cutting edge, comprehensive understanding of the mechanisms for tumor immune evasion that will provide essential data for developing new and better immunotherapies for MCC.

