4.4 Staggering and Dose Escalation

At least three patients will be treated on part I. In part I, patients will be treated with a lower-dose first infusion. Each part I patient must complete their dose-limiting-toxicity (DLT) evaluation period (28 days) after their first T cell infusion before the next part I patient may receive their first infusion. This allows for an ample buffer/window to evaluate for potential cytokine release syndrome and/or neurotoxicity, before proceeding to next patient. After three patients have received their first T cell infusion and completed the 28 day DLT evaluation after the lower first dose infusion, with one or fewer patients experiencing grade 3-4 d related adverse events as defined in **Section 12**, the study may move to part II. If two or more of the first three patients have a treatment-related grade 3 or 4 toxicity, or if any of the first three patients experiences a treatment-related death, at that point the trial will be immediately suspended. We will consult with the data and safety monitoring board (DSMB), and a detailed review of the potential causes of toxicity undertaken. We will reconvene with the DSMB and consideration will be given to changing the cell dose or construct if the T cells were implicated. In that scenario, the dose escalation will be restarted and an additional three patients treated before proceeding to the part II portion of the study. Part I will continue until 3 patients are treated at the lower dose level. If the manufacturing process is short of the intended dose targeted for the patient, whatever smaller dose is available from a single manufacturing run will be given.

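### The Section 13.2.2 toxicity list pools the three reduced-dose part I patients with the full-dose patients, so from the fourth part II patient onward it reacts late to full-dose toxicity

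*Combined protocol and SAP*

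**What the plan says.** Section 13.2.2 (Definition of success and probability of suspension) sets the criterion: "Evidence of excessive toxicity will be an observed proportion of toxicities for which the associated lower 80% confidence limit exceeds 40" per cent. It then gives the working list: "Operationally, this limit will be met if any of the following proportions is observed: 2/2, 3/3-4, 4/5-6, 5/7-8", followed by 6/9-10, 7/11-12, 8/13-14 and 9/15-16. The operating characteristics are "if the true probability of toxicity is 20%, the probability of suspension is approximately 0.06" and "If the true probability of toxicity is 60%, the probability of suspension is approximately 0.84 (based on 5,000 simulations").

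The same section splits the sample into three part I patients and up to 13 in part II. Its closing paragraph applies the rule to everyone: "The above toxicity considerations above will be examined among all patients". Nothing restarts the count at part II.

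On dose, Section 1 (Background) says that in part I "participants will receive a lower dose of T cells for first infusion (5-fold dose reduction from target dose"). Sections 6.1 and 6.4 allow part I patients a second infusion at up to the part II dose.

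Section 4.4 adds two gates. The trial suspends if two or more of the first three part I patients, or two or more of the first three part II patients, have a qualifying toxicity, or on any treatment-related death among them. Once the first three part II patients pass, staggering is lifted.

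**The concern.** A list that ends at 16 must include the three part I patients. Because part II opens only if at most one of those three had an event, they enter the count as a favourable block. If toxicity rises with cell dose, which is the possibility that escalation guards against, these patients dilute the full-dose count and the boundary is reached later at the dose under test.

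The stated 0.06 and 0.84 do not show this, since they take one toxicity rate for all 16 patients and leave out the Section 4.4 gates. Safety is a primary endpoint, and Section 14.2 ties the DSMB's judgement of excessive toxicity to Section 13. The question is how much full-dose toxicity can accrue before the plan's own rule calls for review.

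**Working it through.** **Inputs.** From Section 13.2.2: the list, the 40% limit, the 80% lower confidence limit, and the 3 + 13 split. From Section 4.4: the two-of-three gates (deaths not modelled; a qualifying event is treated as the same in 4.4 and 13.2.2). Assumed, because the documents give no dose-specific rates: part I rate pI from 10% to 40%, part II rate pII up to 70%.

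**1. Reproduce the list.** Let L(x, n) be the one-sided 80% Clopper-Pearson lower limit, which solves P(X ≥ x | n, L) = 0.20. The smallest x with L > 0.40 equals the printed boundary b(n) at every n from 2 to 16. For example, L(8, 13) = 0.461 and L(9, 16) = 0.427, but L(8, 16) = 0.368.

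**2. Reproduce the stated probabilities.** Let f(n, x) be the probability of being unsuspended with x events after n patients:

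f(n, x) = f(n−1, x)(1 − p) + f(n−1, x−1)p,

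moving all mass with x ≥ b(n) to suspended after each patient. With one rate for all 16, this gives 0.062 at 20% and 0.847 at 60%, against the stated 0.06 and 0.84. Running the list over 13 patients gives 0.794 at 60%, so the stated figures come from a pooled series of 16 at a common rate. Adding both Section 4.4 gates gives 0.198 and 0.920.

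**3. What the pooled list requires at full dose (no assumed rates).** After 0/3 in part I, the kth part II patient is patient k + 3 of the list:

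| Part II patient k | Full-dose events needed, pooled: b(k+3) | Counted within part II: b(k) |
|---|---|---|
| 4 | 5 (impossible) | 3 |
| 6 | 6 | 4 |
| 8 | 7 | 5 |
| 9 | 7 | 6 |
| 11 | 8 | 7 |
| 13 | 9 | 8 |

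Suppose part II begins 1/3, which passes Section 4.4, and every later patient has an event. The pooled count runs 2/7, 3/8, 4/9, 5/10, 6/11, 7/12 and first meets the list at 7/12, which is 7/9 at full dose. Just before that, 6 of 8 full-dose patients (75%) have had events without suspension. Counted within part II, the list triggers at 4/6.

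At the end of the trial, 8/13 full-dose events (62%) after 0/3 is 8/16 pooled, below the 9 required.

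**4. Suspension probability with separate rates.** The same recursion, with p = pI for patients 1-3 and pII afterwards:

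| pI / pII | List alone | List + 4.4 gates (as written) | Also counted within part II |
|---|---|---|---|
| 20% / 20% | 0.062 | 0.198 | 0.203 |
| 30% / 30% | 0.177 | 0.391 | 0.409 |
| 40% / 40% | 0.377 | 0.600 | 0.632 |
| 20% / 40% | 0.185 | 0.439 | 0.491 |
| 10% / 60% | 0.493 | 0.733 | 0.833 |
| 20% / 60% | 0.572 | 0.767 | 0.846 |
| 40% / 60% | 0.720 | 0.845 | 0.889 |
| 60% / 60% | 0.847 | 0.920 | 0.939 |

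Hand check at 20%/60%. The part I gate stops with probability 3(0.2²)(0.8) + 0.2³ = 0.104. Given passage to part II, suspension there is 0.740 as written and 0.828 with the part II count. So 0.104 + 0.896 × 0.740 = 0.767, and 0.104 + 0.896 × 0.828 = 0.846.

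Expected full-dose patients treated up to suspension (zero if part I stops): 0.896 × 5.91 = 5.3 as written and 0.896 × 5.33 = 4.8 with the part II count.

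**5. The worst-affected path.** From 0/3 and 1/3 at a true 60%, later suspension has probability 0.19 pooled and 0.57 with the part II count. At 20%/60% this path has probability 0.512 × 0.288 = 0.15. From 1/3 and 1/3 the contrast is 0.44 against 0.57.

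**The case against.** The strongest reply is that Section 4.4 already supplies a full-dose rule. It is stricter than the list for the first three part II patients (two of three, against 3/3) and is unaffected by pooling. This stands. A reader might set the list-alone 0.57 at 20%/60% against the stated 0.84 and infer a loss of 27 points. The documents do not support that reading, because the trial will not run on the list alone. Nor is 0.77 against 0.84 a fair comparison: 0.84 omits the gates, and with them a common 60% gives 0.92. The like-for-like contrast is 0.77 against 0.85.

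The size also depends on an assumed tripling of toxicity between doses. Section 13.2.1 counts toxicity from any study treatment, and interferon gamma and checkpoint inhibition do not differ by part, which narrows any difference. At 40%/60% the rules as written already give 0.845. If the two rates are equal, pooling introduces no bias. Part I patients may also receive the part II dose later, so they are not purely low-dose.

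There is other oversight: suspension of enrolment for patients not given a checkpoint inhibitor after a single toxicity (13.2.2), and monthly review and ad hoc DSMB meetings (14.2). None of these is a general numeric boundary for full-dose patients.

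A reader might also infer that patients treated before a redesign stay in the count and distort it. Section 4.4 says only that "the dose escalation will be restarted and an additional three patients treated before proceeding to the part II portion of the study"; no text says whether earlier patients are carried forward. Such a cohort also follows toxicities or a death, so in general it would not be an event-free block. That inference is not part of this point.

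**Conclusion.** The point holds at moderate size. The list is pooled over dose levels. Beyond the third full-dose patient it is the only general numeric boundary, and it can leave unsuspended a full-dose result (8/13) that the plan's own criterion calls excessive. That much needs no assumed rates.

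The average effect does need them. At 20%/60% with the gates, the shortfall in suspension probability is about 8 points, or about half a full-dose patient. It is 10 points if the part I rate is 10%, and 4 points if it is 40%. Full-dose second infusions in part I patients were not modelled and would reduce the dilution.

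The stated 0.06 and 0.84 are correct for the list alone at a common rate but do not describe the rules as a whole, which give 0.20 and 0.92. This should be fixed. The gain is too small, and too dependent on assumed rates, to call the design unsound without it.

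**What to change.** In Section 13.2.2, add a sentence applying the same list to part II patients, counted from zero, in addition to the pooled list. Restate the suspension probabilities with the Section 4.4 gates included, for equal part I and part II rates and for a part I rate below the part II rate.

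The work is one sentence and a re-run of the simulation. The statistical cost is a higher chance of suspension for DSMB review at rates the plan accepts: +0.005 at a common 20%, +0.02 at 30%, +0.03 at 40%, and +0.05 at 20% in part I with 40% in part II. The sponsor should state these costs beside the gain at 60%.

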For the first three patients treated on part II, the staggering interval will continue as for part I, with each treated patient completing their 28-day DLT evaluation period after first T cell infusion before the next part II patient may be treated at that dose. If two or more of the first three part II patients have a treatment-related grade 3 or 4 toxicity, unless a toxicity specifically accepted in **Section 12.5 and 12.6**, or if any of the first three patients experiences a treatment-related death, at that point the trial will be immediately suspended. We will consult with the data and safety monitoring board (DSMB), and a detailed review of the potential causes of toxicity undertaken. We will reconvene with the DSMB and consideration will be given to changing the cell dose to the part I dose level and/or other protocol modifications on guidance of the DSMB. If instead three part II patients have received their first T cell infusion and completed the 28 day DLT evaluation after the lower first dose infusion, with one or fewer patients experiencing grade 3-4 related adverse events as defined in **Section 12**, staggering restrictions will be lifted and there will be no specific staggering requirement.

As patients eligible for second infusion will have tolerated a previous exposure to the same T cell product, between-patient staggering intervals will not apply for second infusion. However, patients will be monitored for a second 28-day DLT period and safety events recorded. Patients previously treated with lower doses of T cells on earlier versions of this trial will be eligible to receive up to an additional 2 doses of TCR transgenic T cells, starting at the dose level for newly entering patients provided that they meet eligibility criteria in **Section 5** before each additional dose.

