14.2 Monitoring the Progress of Trial and Safety of Participants

The first level of trial oversight for this protocol will be provided by the Principal Investigator, the Research Nurse, and the Research Coordinator(s), who will provide continuous oversight of the trial. These individuals will meet at least monthly to review recently acquired data, stopping rules, and adverse events. Serious adverse events will be reviewed upon occurrence to ensure prompt and accurate reporting to the IND Sponsor, appropriate committees, and regulatory agencies as described above. The data recorded in the research charts and protocol database will be compared with the actual data available from the medical record and/or clinical histories. Data detailed in the research case report forms (CRFs) will include the nature and severity of all grade 3-5 adverse events. The Principal Investigator and all other investigators on the protocol have received formal training in the ethical conduct of human research.

The IND Sponsor will ensure routine trial monitoring as described above and will review Serious Adverse Events and other reports of safety issues promptly upon receipt from the PI.

A DSMB will be in place and will meet after three patients have received treatment (or sooner if requested) to review the data as it relates to AEs and determine whether trial may proceed to part II dose level. The purpose of the DSMB meetings is to review the conduct of the trial to date and assess safety and toxicity of the study intervention. The DSMB will review all grade 3 or greater CTCAE v5.0 toxicities and SAEs and determine whether the study should be prematurely discontinued due to excessive toxicity consistent with **Section 13**. Ad hoc meetings may be scheduled as needed.

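### After the first three patients of each part, a single treatment-related death does not automatically suspend the trial unless it brings the toxicity count to the general boundary

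*Combined protocol and SAP*

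**What the plan says.** The death rule is stated three times, always for a group of three.

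- Section 4.4, part I: "or if any of the first three patients experiences a treatment-related death, at that point the trial will be immediately suspended".
- Section 4.4, part II: the sentence opens "If two or more of the first three part II patients have a treatment-related grade 3 or 4 toxicity" and goes on to the same death clause. That clause does not itself name part II; the sentence around it supplies the scope.
- Section 13.2.2: "If any of the first three patients experience treatment related death, the trial will be suspended". This follows the part I rule. The section then has no death rule for part II, although it says that "the remaining (up to) 13 pts will be treated on the part II portion of the trial".

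Once three part II patients have passed their 28-day evaluation with at most one event, 4.4 says "staggering restrictions will be lifted and there will be no specific staggering requirement".

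The other provisions that could act on a later death are these:

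- **General boundary (13.2.2).** "Operationally, this limit will be met if any of the following proportions is observed: 2/2, 3/3-4, 4/5-6, 5/7-8, 6/9-10, 7/11-12, 8/13-14, 9/15-16". Section 13.2.1 counts any related grade 3 or higher event, with listed exceptions, so a grade 5 event adds one to the count.
- **Patients not receiving a checkpoint inhibitor (end of 13.2.2).** A toxicity in one of them suspends enrollment of such patients until the DSMB and PI have reviewed it. There is no time limit on this rule.
- **Reporting and review (12.7.2, 14.2).** Fatal events go to the sponsor's Medical Monitor within 24 hours. Serious events are reviewed as they occur, and the DSMB reviews all grade 3 or higher toxicities and serious events. The only DSMB meeting tied to a patient count is after three patients; beyond that, "Ad hoc meetings may be scheduled as needed".
- **Termination (Section 16).** The PI, sponsor, IRB or FDA may end the study.

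**The concern.** The protocol treats one related death as serious enough to suspend the trial while patients are treated one at a time. That trigger ends when staggering ends, so it is absent in the phase where several patients may be under treatment at once at the part II dose. What then operates automatically across the trial is a rule built to detect a toxicity rate above 40%, which is not designed to react to a single death.

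Sections 4.4 and 13.2.2 also differ. Section 14.2 asks the DSMB to judge early discontinuation consistently with Section 13, and Section 13 lacks the part II death rule. A board working from Section 13 would find a death trigger for three patients; a board working from 4.4 would find one for six.

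At stake is whether infusions continue in other patients between a related death and the DSMB's review of it.

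**Working it through.** **1. Reproducing the plan's figures.** Inputs: up to 16 patients (13.1) and the boundary list (13.2.2). Each listed pair has a one-sided 80% Clopper-Pearson lower limit above 40%; for 2/2 it is 0.20^(1/2) = 0.447, and for 9/16 it is 0.427. An exact binomial recursion, applying the list after each patient from the second, gives:

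| True toxicity rate | Stated probability of suspension | Recomputed |
|---|---|---|
| 20% | 0.06 | 0.062 |
| 60% | 0.84 | 0.847 |

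The stated figures are reproduced from the list alone, so they include no death rule.

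**2. Patients outside the death rule.** Under 4.4: 16 - 3 - 3 = 10 (patients 7 to 16), if all 16 are treated and part I is not restarted. Under 13.2.2 alone: 16 - 3 = 13.

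**3. Distance to the general boundary from patient 7.** Consecutive events needed:

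| Events in patients 1-6 | Path | Consecutive events needed |
|---|---|---|
| 0 | 1/7, 2/8, ... 7/13 all below; 8/14 reaches it | 8 |
| 1 | 2/7, ... 6/11 below; 7/12 reaches it | 6 |
| 2 | 3/7, 4/8, 5/9 below; 6/10 reaches it | 4 |
| 3 | 4/7 below; 5/8 reaches it | 2 |

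If neither two-of-three rule in 4.4 has been met, at most 1 + 1 = 2 of the first 6 have an event. The last row then needs an event that arrived after those decisions.

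**4. How often a single later death would itself reach the boundary.** The recursion is conditioned on no earlier boundary crossing and no two-of-three stop in part I. The death is placed at each of patients 7 to 16 in turn and the results averaged:

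| True grade 3+ toxicity rate | Mean over patients 7-16 | Highest (patient 8) |
|---|---|---|
| 20% | 0.2% | 0.9% |
| 25% | 0.5% | 2.0% |
| 40% | 3.0% | 8.9% |

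These are upper figures. Applying the part II two-of-three rule as well removes patient 8 (at most 2 + 2 = 4 of 8, below 5) and lowers the means to about 0.04%, 0.1% and 1.2%.

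**5. Chance that the gap is met.** The documents give no related-death rate, so q is an assumption. P(at least one in m patients) = 1 - (1 - q)^m:

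| q | m = 10 | m = 13 |
|---|---|---|
| 2% | 1 - 0.98^10 = 18% | 23% |
| 5% | 1 - 0.95^10 = 40% | 49% |
| 10% | 1 - 0.90^10 = 65% | 75% |

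**6. Reach of the subgroup pause.** Section 13.1 expects about 12 patients on a checkpoint inhibitor, so about 16 - 12 = 4 without. If spread evenly, that is 4 × 10/16 = 2.5 of the last 10. It pauses enrollment of that subgroup only.

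**The case against.** The strongest reply is that later deaths are far from ignored. Section 14.2 requires review of serious events on occurrence, monthly team review of adverse events and stopping rules, and DSMB review of all grade 3 or higher toxicities with a decision on discontinuation. Section 12.7.2 requires 24-hour notice of fatal events and evaluation by the Medical Monitor. In practice a related death would very likely prompt a halt. Section 14.1 also refers to a DSMB Charter, which is not among the documents and may set event triggers.

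All of that stands, and it rules out three stronger readings that a reader might infer:

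- **That a later death triggers no pause at all.** Not supported. A toxicity in a patient without a checkpoint inhibitor suspends enrollment of that subgroup, and a death that brings the count to the boundary suspends the trial.
- **That related deaths could go unreviewed.** Not supported. Review is mandatory; what is missing is an automatic hold on further infusions until the DSMB has reviewed.
- **That the product is first-in-human here.** Not supported. Sections 2.1.12 and 2.2.1 describe patients treated on earlier versions of the trial, including three at similar doses with no toxicity attributed to the cells. Those versions used radiation or chemotherapy, not interferon gamma, for class I MHC upregulation.

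The run of seven events to 7/13 is likewise a property of the boundary and not a forecast, since others would be expected to act well before.

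None of this supplies the missing trigger. The provisions cited are reports, reviews or discretionary powers, and the protocol itself thought an automatic suspension necessary for the first patients of each part.

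**Conclusion.** The point holds in this form: after the first three patients of each part, no rule in the protocol automatically suspends the whole trial for one treatment-related death unless that death brings the count to the general boundary. The gap covers 10 of 16 patients under 4.4, or 13 of 16 on 13.2.2 alone, and the two sections need reconciling in any case. The boundary is a poor substitute: on average a single later death would reach it at most 0.2% of the time at 20% true toxicity and 3.0% at 40%.

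The counts assume that all 16 patients are treated and part I is not restarted. The 18%, 40% and 65% rest on assumed death rates and include the few patients covered by the subgroup pause. The conclusion concerns the protocol text; the DSMB Charter could already close the gap, but it cannot be checked here.

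**What to change.** 1. Reconcile 4.4 and 13.2.2 so that both state the same death rule, including the part II rule that 13.2.2 omits.
2. In both sections, extend the existing trigger to any treated patient, for a death judged related to study treatment within the adverse event collection period of 12.5. That bound keeps the rule from running through the 15-year follow-up.
3. State the consequence for these later patients as suspension of enrollment and new T cell infusions pending DSMB review, with any later change left to the DSMB. Do not carry over the part-specific consequences in 4.4 (restarting escalation, considering the part I dose level), which are not defined for patients 7 to 16.
4. In 14.2, make an ad hoc DSMB meeting mandatory on this trigger, and align the wording with the DSMB Charter.
5. Leave the boundary list unchanged, and note beside 0.06 and 0.84 that they are for that list alone and include no death rule.

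The cost is a few sentences in 4.4 (both parts), 13.2.2 and 14.2, with no extra patients or procedures. The downside is a possible accrual pause and a higher overall chance of suspension. The increase under 4.4 cannot exceed the chance of at least one related death in patients 7 to 16, so it is small if such deaths are rare.
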